3. GENERAL ANALYSIS AND REPORTING CONVENTIONS

The following is a list of general analysis and reporting conventions to be applied for this study. If departures from these general conventions are present in the specific evaluations section of this SAP, then those conventions will take precedence over these general conventions.

- All analysis will be performed using the SAS System version 9.4 or later.
- All subject data listings and summary listings will be sorted for presentation in order of treatment group and subject number in the following order: BLXA4-ME rinse, placebo rinse, and non-rinse control.
- Missing values for both numeric and character variables will be presented as blanks in a table or listing.
- Mixed case will be used for all titles, footnotes, column headers, and programmer-supplied formats.
- All date values will be presented as DDMMYY YYYY (e.g. 21AUG2008) format. A 4-digit year is required for all dates. Partial dates will dashes to represent missing days or months (e.g. - -JUL2009).
- All observed time values will be presented using a 24-hour clock HH:MM format (e.g., 01:35, or 17:26).
- Population sizes will be presented for each treatment group in the column heading as (N=XX).
- The sample size (n) shown as a summary statistic will be the number of subjects with non-missing values.
- Categorical variables will be summarized using counts (n) and percentages (%) and will be presented in the form n (%). All summaries for categorical variables will include all categories, even if none of the subjects had a response in a particular category, to ensure completeness. Continuous variables will be summarized using descriptive statistics: n, mean, median, standard deviation (SD) or standard error (SE), minimum, and maximum. The mean and median will be reported at 1 more significant digit than the precision of the data. The SD and/or SE will be reported at 2 more significant digits than the precision of the data. The minimum and maximum will be reported to the same level of precision as the original observations.
- Calculated variables will not be rounded prior to analysis. Rounding will only occur after analysis. If any values are calculated to have more significant digits than the original data, then the value will be rounded so that it is the same level of precision as the original data.
- P-values will be reported to 3 decimal places if greater than 0.001. If less than 0.001 then p-values will be reported as '<0.001'.

4. ANALYSIS POPULATIONS

The exclusion criterion of periodontitis was removed in October 2015 for Protocol Version 4.0. This will possibly change the study population. To explore the possible effects of including study participants with periodontitis, sensitivity analyses will be performed as described in section 9.3.2.2.

4.1 Safety Population

The Safety Population will consist of all subjects who are randomized into a study arm and complete their Baseline Visit. For the safety evaluations, subjects will be analyzed according to the treatment actually received. Any subjects that in error were administered both the BLXA4-ME and the placebo rinse at different times during the study will be analyzed in the BLXA4-ME treatment arm. Subjects that in error were administered both the non-rinse control treatment and either the BLXA4-ME or placebo rinse will be analyzed according to the rinse administered.

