6.2 Dosage, Preparation, and Administration of Study Product

ClinRinse-1 containing 1.0 μM BLXA4-ME and placebo rinse will be provided to study participants in the original bottles supplied by Avanti. A 30 mL polypropylene dosing cup with volume markings will be provided with the rinse. Subjects will rinse under supervision on the day they pick up study drug. They will be instructed to use the rinse (30 mL for 45 seconds) daily after brushing their teeth in the morning. Subjects will be provided with a timer so that 45 seconds of use can be standardized. Subjects will be resupplied with study drug on Days 3, 7, 14, and 21.

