7.3 Enrollment/Baseline

Study Visit 1 - Enrollment/Baseline Visit (Day 0)

- Obtain and document consent from subject on study consent form.
- Review and confirm medical and dental history, including alcohol and tobacco use history, for study inclusion.
- Record vital signs (temperature, pulse rate, respiratory rate, blood pressure).
- Record current concomitant medications and dental procedures and update medication history for study inclusion.
- Obtain urine pregnancy test on women of childbearing potential. Study staff will record the test kit lot, expiration date, and result. Test must be documented as negative before continuing to conduct baseline procedures that follow.
- Perform intraoral and extraoral examinations, to include hard and soft tissue assessments (face, lymph nodes, lips, buccal mucosa, floor of the mouth, tongue, hard and soft palate, gingiva, edentulous ridges, and teeth).
- Collect GCF for baseline measurements of IL-1 β .
- Assess and record baseline MGI.
- Assess and record baseline PI.
- Obtain supragingival plaque samples for baseline analyses of oral bacteria.
- Assess and record baseline PD and GM-CEJ distance (to calculate CAL).
- Assess and record baseline BOP.
- Reconfirm eligibility prior to subject randomization based on information collected during Screening Visit and study Visit 1.
- Obtain approximately 15 mL blood for baseline BLXA4 level and specialized pro-resolution mediator (SPM) (lipoxins and resolvins) profiling.
- Randomize subject to 1 of the study arms, using a block randomization schedule.
- Provide study drug with instructions for use and a timer to be used while rinsing. A study team member other than the examiner will supervise the subject's first use of the medication.
- Provide subject with the memory aid and instructions for its use.
- Provide subject with a study contact number to call for AEs or questions.

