9.3.2 Expectedness

This trial involves the first use of the BLXA4-ME oral rinse in humans; therefore, no human data exist to classify expectedness of events. In a preclinical 28-day oral irritancy study in rats, transient erythema and edema of the oral mucosa were noted in animals treated with either BLXA4-ME or a saline solution used as a control. For this study, the IND sponsor, the study investigator, and the NIDCR medical monitor will be responsible for assessing AEs that may be related to product use. An AE will be considered unexpected if the nature, severity, or frequency of the event is not consistent with the risk information described in the protocol or the Investigator's Brochure or discussed with the subject during the informed consent process.

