8.4 Adverse Events

All AEs will be coded to a system organ class (SOC) and preferred term (PT) using the most current version of the Medical Dictionary for Regulatory Activities (MedDRA). All tabular AE summaries will be for TEAEs. TEAEs will be defined as those AEs with an onset on or after the date of first dose of study drug (study visit 1: Day 0). If an AE was recorded prior to the first dose of study drug and there was an increase in its severity, the AE will be considered a TEAE. All other AEs will be classified as non-treatment-emergent. Treatment-emergent AEs will be flagged in all AE data listings.

An overall summary table will be developed to report the number of events and the incidence of participants having at least one event in the following categories:

- TEAEs
- TEAEs indicated as serious (SAEs)
- TEAEs that lead to study drug discontinuation
- TEAEs with an outcome of death
- TEAEs that were reported as having a definite/certain or possible relation to study drug
- TEAEs reported as having a severity rating of severe

In addition, a summary table of TEAEs classified by system organ class (SOC) and preferred term (PT) will be provided for each of the following:

- TEAEs
- TEAEs by maximum severity
- TEAEs by relationship to study drug

The summary of all TEAEs will present both the number of TEAEs and the incidence of TEAEs. The summary of TEAEs by severity, relationship to study drug, and week of treatment will only report the incidence of TEAEs. When reporting the number of TEAEs, if the same TEAE occurs for a subject on multiple occasions the event will be counted once for each occurrence. When reporting the incidence, a subject will only be counted once if they ever experience an event within the SOC and ever experience the individual PT.

For the summary of TEAEs by severity, if the severity of the TEAE is not reported, then the severity of the TEAE will be counted as severe. If the same TEAE occurs for a subject on multiple occasions, the TEAE will be categorized according to the highest severity rating for that TEAE in that subject. For the summary of TEAEs by relationship to study drug, if the relationship is missing, it will be counted as definite/certain. If the same TEAE occurs for a subject on multiple occasions, the TEAE will be categorized according to the closest relationship to study drug reported for that TEAE in that subject.

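### Safety Population membership depends on completing the Baseline Visit, during which the first rinse is taken, so on a literal reading an exposed subject can drop out of the safety tables

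*SAP*

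**What the plan says.** Protocol 12.2.1 and SAP 4.1 use the same definition of the Safety Population: "all subjects who are randomized into a study arm and complete their Baseline Visit". Use of product is not a criterion, and neither document says what completing the visit means. SAP 4.1 adds that safety is analysed by the treatment a subject really got. Its other additions, and SAP section 11, deal only with subjects given the wrong treatment.

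Protocol 7.3 (Day 0) lists the baseline assessments, the blood draw, randomization and dispensing, and then states: "A study team member other than the examiner will supervise the subject's first use of the medication". Protocol 6.2 agrees: "Subjects will rinse under supervision on the day they pick up study drug". Two items follow in the 7.3 list: "Provide subject with the memory aid and instructions for its use" and "Provide subject with a study contact number to call for AEs or questions".

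SAP 8.1 and Protocol 12.5.1 tie the safety analyses to the Safety Population. SAP 8.4 opens the treatment-emergent window at first dose: "TEAEs will be defined as those AEs with an onset on or after the date of first dose of study drug", which it identifies as Visit 1, Day 0. Protocol 5.5.2 replaces subjects who withdraw before Day 14.

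**The concern.** Membership of the primary analysis set is decided by something that happens after exposure. A subject who has an immediate oral reaction to the supervised rinse and walks out has used the product but, on the literal wording, has not completed the visit. That subject leaves both the numerator and the denominator of the safety tables.

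This loss works in one direction: it understates acute reactions. The no-rinse arm has no product to react to, so loss by this route can occur only in the two rinse arms. Safety is the primary outcome (Protocol 3.2.1), and oral irritation is the risk named in Protocol 2.5.1. Protocol 9.3.2 adds: "This trial involves the first use of the BLXA4-ME oral rinse in humans". Protocol 12.3 and SAP 2.5 justify the sample size by the chance of seeing at least one event of a given kind, so the step from none observed to one observed is the step the design is built to detect.

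**Working it through.** **1. The plan's own figure.** SAP 2.5 gives 87.1% as the chance of at least one event among 40 subjects when the true rate is 5%. Check: 1 − (1 − 0.05)^40 = 87.15%. It reproduces. The point disputes no stated number; it concerns who is counted.

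**2. Following one subject through the documents.** Assume a subject is randomized to a rinse arm, takes the supervised rinse on Day 0, reacts and leaves.

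| Question | Source | Answer |
|---|---|---|
| Exposed? | Protocol 6.2, 7.3 | Yes |
| Event treatment-emergent? | SAP 8.4 | Yes, onset on the date of first dose |
| Visit completed? | Protocol 7.3 | No, if every listed item counts; yes, if only the baseline assessments count |
| In the Safety Population? | Protocol 12.2.1, SAP 4.1 | Depends on the previous row |
| In the safety summaries? | Protocol 12.5.1, SAP 8.1 | Only if in the Safety Population |
| In the disposition table? | SAP 5.1 | Yes, with the reason for leaving |
| Replaced? | Protocol 5.5.2 | Yes |

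Under the strict answer in the third row, SAP 8.4 classes the event as treatment-emergent while the population rule removes the subject from the table meant to show it.

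**3. Size, by assumption.** The documents give no rate of immediate reaction followed by leaving. Assume k test-arm subjects do this and nobody else in the arm has the event. The exact one-sided 95% upper bound U for x events in n solves P(X ≤ x | n, U) = 0.05. For x = 0 this is U = 1 − 0.05^(1/n).

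| Case | Current rule, strict reading | Exposure-based rule |
|---|---|---|
| k = 1, no replacement | 0/49, U = 5.9% | 1/50 = 2.0%, U = 9.1% |
| k = 2, no replacement | 0/48, U = 6.1% | 2/50 = 4.0%, U = 12.1% |
| k = 2, both replaced | 0/50, U = 5.8% | 2/52 = 3.8%, U = 11.6% |

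The k = 2 row with replacement is the one that follows Protocol 5.5.2: 52 are randomized to the arm, 2 are dropped, and 50 remain.

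**4. How likely is at least one such subject?** With 50 exposed, the chance is 1 − (1 − q)^50. For assumed q of 0.5%, 1%, 2% and 5% it is 22%, 39%, 64% and 92%. The range is wide because q is unknown. These figures do not show that the event is expected.

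**The case against.** The exclusion needs a strict reading of an undefined word. Every baseline clinical assessment, the blood draw and randomization are listed before the rinse, and only two hand-outs come after it. The list in Protocol 7.3 does not say that its order is binding. A sponsor could reasonably treat the visit as complete, and both the Day 0 start of the treatment-emergent window and the by-treatment-received rule in SAP 4.1 favour that reading. This stands: the documents do not show that any dosed subject will be dropped. But they do not rule it out either, and the choice would then be made case by case after the event is known.

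A reader might infer that the subject disappears from all safety evaluation. The documents do not support that. Adverse event, serious event and unanticipated-problem capture (Protocol section 9), safety follow-up of those who withdraw (Protocol 5.5.2 and 7.7), the suspension rules (Protocol 9.5) and the disposition table (SAP 5.1) do not depend on the analysis set. Only the summary tables and their denominators are affected.

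A reader might also infer a distorted comparison of test with placebo rinse. That is weak, because the placebo is the same formulation without the active compound. Irritation caused by the vehicle would affect both rinse arms.

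Finally, confidence bounds on event rates are not among the outputs described in SAP 8.4, and Protocol 12.1 plans no formal testing in the primary safety analysis. The bounds above only give a sense of scale.

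**Conclusion.** The point holds as a defect of definition, of minor severity. The primary safety set carries a condition that is settled after exposure, and no other rule in either document keeps a dosed subject who leaves before the Baseline Visit ends. The effect is confined to the safety summaries and can only understate immediate reactions.

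Its size rests on three assumptions: that such a subject occurs, that the visit is judged incomplete, and that no other subject in the arm has the same event. Under these, two cases with replacement turn 2/52 into 0/50 and roughly halve the upper bound, from 11.6% to 5.8%. Few cases are likely, and there may be none. Sample size and power are unaffected.

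**What to change.** In Protocol 12.2.1 and SAP 4.1, define the Safety Population as all randomized subjects who used any amount of study rinse, plus all subjects randomized to no rinse, regardless of whether the Baseline Visit was completed. Keep the existing SAP 4.1 rule of analysing safety by the treatment received. Record the change in SAP section 11.

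The cost is one sentence in each document. No procedure, visit, sample size or other analysis has to change. It should be done before database lock, when the blind is broken (SAP 2.4), so that no decision on inclusion is made with treatment known.

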4.2 Efficacy Population

The Efficacy Population will consist of all subjects of the Safety Population who have a baseline and at least 1 post-baseline assessment of 1 or more of the secondary efficacy outcome measures. Subjects that dropout or withdraw prior to Day 14 will be replaced in the efficacy population. For the efficacy evaluations, subjects will be analyzed according to the treatment actually received. Any subjects that began the study administering the treatment for one of the study arms and then later in error switched treatments to another study arm will not be included in the efficacy population.

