4 STUDY DESIGN

This Phase 1/2 study comprises 3 groups in a randomized, placebo-controlled, double-blind clinical trial design. Subjects will be healthy adults, aged 18 through 65 years, with gingivitis as defined by MGI \geq 2.0. The treatment group (1.0 μ M BLXA4-ME oral rinse) and the placebo rinse group will each consist of 50 subjects. The no-rinse control group will consist of 25 subjects. The group sizes allow for a 20% dropout rate.

The treatment group will receive the active agent BLXA4-ME at a concentration of 1.0 μ M in an oral rinse applied once daily (after morning teeth brushing) for 28 days. The placebo rinse control subjects will rinse once daily after morning teeth brushing with the same rinse formulation, except that it will not contain BLXA4-ME. The no-rinse control group will use no oral rinse to assess the effect of the rinsing action independent of the active ingredients. At the Enrollment/Baseline Visit, eligible individuals will be randomly assigned to 1 of the 3 treatment groups. The baseline clinical measurements, i.e., MGI, probing depth (PD), CAL, PI, and BOP, will be recorded. Plaque, GCF, and blood will be collected as described in the Manual of Procedures. The subjects randomized to rinse groups will be given the BLXA4-ME oral rinse formulation or

placebo rinse with instructions for use in addition to their regular oral hygiene. Subjects in all groups will be instructed to maintain their regular oral hygiene procedures, except for using the study-provided rinse, if applicable.

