5.4.2 Masking Procedures

The examiner will be masked to the assigned treatment. Subjects receiving oral rinse will not know whether they are in the active or placebo rinse group. A qualified and trained individual not involved in the examination procedures will be responsible for making assignments to treatment groups, dispensing the products to the subjects with instructions, collecting information on subject compliance, and soliciting AE reports from subjects.

Test materials will be coded and the identity of the products concealed, so the examiners and subjects will remain blinded. Subjects will be reminded to avoid discussing product use with their examiners at any time during their participation.

The product code may be broken for an individual subject if he or she experiences a serious adverse event (SAE) and cannot be adequately treated without knowing the identity of the study product. Every effort will be made to inform the study investigators prior to breaking the blind, or in the event of an emergency, as soon as possible thereafter.

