5.5 Subject Withdrawal

5.5.1 *Reasons for Withdrawal*

Subjects are free to withdraw from participation in the study at any time upon request.

An investigator may terminate a study subject's participation in the study if:

- Any clinical AE, laboratory abnormality, or other medical condition or situation occurs such that continued participation in the study would not be in the best interest of the subject.
- The subject meets an exclusion criterion (either newly developed or not previously recognized) that precludes further study participation.

5.5.2 *Handling of Subject Withdrawals or Subject Discontinuation of Study Intervention*

Should a subject elect to withdraw from the study and cease use of product, efforts will be made to complete as much follow-up of safety information as possible. Telephone contact with the subject is acceptable if it is not possible to arrange a follow-up appointment. Subjects who withdraw prior to the Day 14 Visit will be replaced.

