2.2 Overall Study Design and Plan

This study has a randomized parallel placebo-controlled double-blind study design with one treatment arm and two control arms (placebo oral rinse, and no rinse controls). Subjects in the treatment (N=50) and placebo rinse (N=50) arms will be double-blinded and receive oral rinse (BLXA4-ME or placebo rinse) to be applied once daily after morning teeth brushing. The no-rinse control arm (N=25) will be blinded from the investigators and apply no oral rinse. Subjects will perform their randomized treatment for 28 days. Safety parameters will be assessed before treatment and at Days 3, 7, 14, 21, and 28 after the initial treatment. Efficacy parameters will be assessed before treatment and Day 14 and Day 28 after the initial treatment. Total duration of subject participation will be 3 months (in clinic visits through 28 days, and a follow-up safety phone call at 2 months after last product use).

The Study Flow Chart and the Schedule of Events can be found in Appendices 13.1 and 13.2, respectively.

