9. EFFICACY EVALUATION

9.1 Overview of Efficacy Analysis Issues

9.1.1 Handling of Dropouts and Missing Data

Subjects that dropout or are withdrawn prior to Day 14 will be replaced in the Efficacy Population. The mixed models analyses (described in the sections below) will automatically adjust for any missing values provided the missing values are missing at random; and thus, no additional imputation is necessary for missing values that are missing at random.

Missing observations are “not missing at random” if their missing-ness is possibly correlated with disease progression or efficacy. Missing efficacy observations due to missed visits or early study withdrawal will be deemed “not missing at random” if there were any treatment-emergent AE (TEAE) prior to or concurrent with a subject’s missed visit and the relationship between the TEAE and study drug was rated as “Possible”, “Probable”, or “Definite”.

If more than 5% of a given efficacy endpoint is missing, or any missing observations are deemed “missing not at random” then a sensitivity analysis will be performed by repeating the given efficacy analysis with all missing values imputed using “last observation carried forward”. The sensitivity analysis will also be triggered if for any other reason the principle investigator suspects that missing values may bias the analysis. The reasons any sensitivity analyses are triggered will be footnoted in the sensitivity analysis tables.

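### The SAP 9.1.1 efficacy missing-data check, on its natural reading, cannot see or include subjects who leave before Day 14 after a related adverse event

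*SAP*

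**What the plan says.** Entry to the Efficacy Population (Protocol 12.2.2, SAP 4.2) is for Safety Population subjects "who have a baseline and at least 1 post-baseline assessment of 1 or more of the secondary efficacy outcome measures". SAP 2.2 sets the timing: "Efficacy parameters will be assessed before treatment and Day 14 and Day 28 after the initial treatment". SAP 9.2.2 and 9.3.2 run all efficacy analyses on that population.

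Replacement is stated three times. Protocol 5.5.2: "Subjects who withdraw prior to the Day 14 Visit will be replaced". SAP 4.2: "Subjects that dropout or withdraw prior to Day 14 will be replaced in the efficacy population". SAP 9.1.1: "Subjects that dropout or are withdrawn prior to Day 14 will be replaced in the Efficacy Population".

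SAP 9.1.1 then sets the check on missing data. It begins "If more than 5% of a given efficacy endpoint is missing, or any missing observations are deemed" and goes on to name data not missing at random, in which case the analysis is repeated with LOCF. A missed visit or early withdrawal falls in that class if a TEAE rated possibly, probably or definitely related came before or with it. The principal investigator may also call for the sensitivity analysis on other grounds. No denominator is given for either trigger.

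SAP 8.2 uses the same two triggers for periodontitis progression, but SAP 8.1 places all safety analyses in the Safety Population: everyone randomised who completes the Baseline Visit.

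On numbers, Protocol 4 says "The group sizes allow for a 20% dropout rate". Protocol 12.3 and SAP 2.5 give 50/50/25 enrolled and 40/40/20 completing.

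**The concern.** Oral irritation is the risk named in Protocol 2.5.1, this is the first human use of the rinse (Protocol 9.3.2), and irritancy is scored from Day 3. Withdrawal for intolerance before Day 14 is therefore plausible, although neither document gives a rate. Such a withdrawal is just what the related-TEAE rule in SAP 9.1.1 is meant to catch, yet the subject has no efficacy value after baseline and so is outside the set to which the rule is applied.

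At stake is the reading of the Day 28 MGI contrast between active and placebo, which SAP 9.3.2.1 ranks first, and of the BOP contrast that follows it. SAP 9.3.2 says that one purpose of these analyses is to estimate the size and variance of the effect for planning later trials. An estimate confined to those who stayed at least until Day 14, with no companion analysis in all randomised, could be somewhat optimistic for that use.

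**Working it through.** **1. The plan's own figures.** Inputs from Protocol 12.3 and SAP 2.5: SD 0.3 at each visit, within-subject correlation 0.3, difference 0.2, alpha 0.05 (two-sided reproduces the stated power), attrition 20%.

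- Enrolment: 40/0.8 = 50 and 20/0.8 = 25.
- SD of change: 0.3 × √(2 × (1 − 0.3)) = 0.355.
- Power against placebo (40 v 40): 70.8% by noncentral t on 194 df, 71.2% by normal approximation; stated 70.9%.
- Power against no rinse (40 v 20): 53.5% and 53.9%; stated 53.8%.

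The figures reproduce.

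**2. One subject traced through both rules.** Take a subject who withdraws on Day 5 after a possibly related TEAE.

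- *Efficacy (SAP 4.2, 9.1.1, 9.3.2.1).* There is no Day 14 or Day 28 value, so the subject is not in the Efficacy Population. The mixed model takes change from baseline as its outcome, so the subject supplies no record to it. The missing values meet the 9.1.1 description of not missing at random but lie outside the set being checked. Repeating the analysis with LOCF on that set does not bring the subject in.
- *Periodontitis progression (SAP 8.1, 8.2).* The subject is in the Safety Population. The same event sets off the sensitivity analysis, and the missing values are imputed as progression.

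The same triggers thus reach this subject in one analysis and not in the other.

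**3. The 5% trigger.** Let e be the share of randomised subjects lost before Day 14, out of 20% lost in all. The documents do not give e. Day 28 missingness within the Efficacy Population is (0.20 − e)/(1 − e). It equals 5% when 0.20 − e = 0.05 − 0.05e, that is e = 0.15/0.95 = 15.8%. Below that, later losses alone set off the trigger.

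**4. Replacement and the total.** If subjects are added until 125 have passed Day 14, the number randomised is 125/(1 − e), and completers per rinse arm are 0.8 × 50/(1 − e).

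| e | Randomised | Completers | Power v placebo | Day 28 missing in Efficacy Population |
|---|---|---|---|---|
| 0% | 125 | 40/40/20 | 70.8% | 20.0% |
| 5% | 132 | 42/42/21 | 73.0% | 15.8% |
| 10% | 139 | 44/44/22 | 75.3% | 11.1% |
| 15% | 147 | 47/47/24 | 77.7% | 5.9% |

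If 125 is instead a cap that includes replacements, completers stay at 40/40/20.

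**5. Size of the shift, under assumed inputs.** Suppose that 10% of the active arm and none of the placebo arm leave early, that stayers differ from placebo by 0.20, and that the leavers would have been between equal to placebo and 0.2 worse.

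- All randomised, leavers equal to placebo: 0.9 × 0.20 + 0.1 × 0 = 0.18.
- All randomised, leavers 0.2 worse: 0.9 × 0.20 − 0.1 × 0.20 = 0.16.
- Ratio of the stayers' figure: 0.20/0.18 = 1.11 and 0.20/0.16 = 1.25.
- Standard error of the contrast at 40 v 40: 0.355 × √(2/40) = 0.079, so the shift of 0.02 to 0.04 is about a quarter to a half of one standard error.

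**The case against.** The case for leaving the plan alone has force. Efficacy is secondary, unadjusted and described as preliminary. Safety is primary, and early leavers stay in the Safety Population. The disposition table (SAP 5.1) shows by arm how many were randomised, how many withdrew and why, and how many are in each population. TEAEs that lead to discontinuation are tabulated and listed (SAP 8.5). The placebo is the same rinse without the compound, so irritation from the vehicle should affect both rinse arms, which makes unequal loss less likely. The principal investigator can also call for the sensitivity analysis. All of this stands and limits the weight of the point. It does not supply an efficacy estimate that includes early leavers: the planned sensitivity analysis repeats the analysis on the same population.

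A reader might infer more than the documents support:

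- *That replacement causes the exclusion.* It does not. The requirement for a post-baseline value does; replacement only refills the count. Deleting the replacement sentences would restore nobody.
- *That the loss is concealed.* The disposition and safety tables show it.
- *That the whole missing-data check falls silent.* With 20% attrition, the 5% trigger still fires from later losses unless about 15.8% or more leave early.
- *That 125 and 40/40/20 are wrong.* They reproduce, the total is given as approximate, and replacement leaves completers and power the same or higher.
- *That a replacement takes the vacated arm, known in advance to the person who makes assignments.* Nothing says so. The only procedure described is block randomisation of enrolled subjects (Protocol 5.4.1, 7.3).

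**Conclusion.** The point holds as a gap between a stated rule and the set it is applied to. SAP 9.1.1 singles out withdrawal after a related TEAE, but on the natural reading its trigger does not count such withdrawals before Day 14. Whatever sets the sensitivity analysis off, it cannot include those subjects. The reading of the trigger is an inference, because the denominator is not stated. The second part follows directly from SAP 4.2 and 9.3.2.

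The possible size is modest: 0.20 in stayers against 0.18 to 0.16 in all randomised, if 10% leave early in the active arm only with the outcomes assumed above. No rate or outcome for early leavers comes from the documents. The shift matters mainly for planning. Since sample size scales with 1/effect², a later trial aimed at the all-randomised effect would need (0.20/0.18)² to (0.20/0.16)², that is 1.23 to 1.56, times as many subjects.

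Two smaller wording gaps remain. The protocol ties replacement to the Day 14 Visit and the SAP to Day 14. With the ±1 day window, a subject assessed on Day 13 who then leaves qualifies under the first sentence of SAP 4.2 and is replaced under the second, though nothing says that the observed data are dropped. Nor does either document say whether replacements count within the 125. This is a cheap improvement, not a fault that threatens the trial's conclusions.

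**What to change.** In SAP 9.1.1, define both triggers over all randomised subjects with a baseline value. Add one sensitivity analysis of Day 28 MGI and BOP in that set, with pre-Day-14 withdrawals in every arm either given baseline carried forward (change of zero, in line with the SAP's own LOCF) or imputed from the placebo arm. Name the choice before unblinding. The two differ if placebo subjects change from baseline: the first sets leavers to no change, the second to no benefit over placebo.

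Use the protocol's wording, before the Day 14 Visit, in SAP 4.2 and 9.1.1, and state that observed Visit 4 data are kept. State whether replacements count within the 125; if they do not, give the expected total (about 132, 139 or 147 for 5%, 10% or 15% early loss).

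The cost is SAP wording, one protocol sentence on the total, and one extra table. The added estimate will usually be slightly less favourable. The SAP is being written before database lock, so the change can still be made in advance.
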